Protocol Number: SGNLVA-005

Version: Amendment 04; 02-Nov-2022

Protocol Title: Open-Label Phase 2 Study of Ladiratuzumab Vedotin (LV) for Unresectable Locally Advanced or Metastatic Solid Tumors

Investigational Product: Ladiratuzumab vedotin

Brief Title: A Study of Ladiratuzumab Vedotin in Advanced Solid Tumors

Phase: 2

IND Number: 117532

EudraCT Number: 2019-001946-17

Sponsor: Seagen Inc.
[name]

Medical Monitor: PPD [REDACTED] MD, PhD
Seagen, Inc
Tel: PPD [REDACTED]
E-mail: PPD [REDACTED]

Study Director: PPD [REDACTED] PharmD
Seagen, Inc
Tel: PPD [REDACTED]
E-mail: PPD [REDACTED]

SAE Email or Fax: See email or fax number specified on the SAE report form.

PROTOCOL SYNOPSIS

Protocol Number SGNLVA-005	Product Name Ladiratuzumab vedotin
Version Amendment 04; 02-Nov-2022	Sponsor Seagen Inc. [name]
Phase 2	

Protocol Title

Open-Label Phase 2 Study of Ladiratuzumab Vedotin (LV) for Unresectable Locally Advanced or Metastatic Solid Tumors

Study Objectives

Primary

- Evaluate antitumor activity of LV as monotherapy (Part A, Part B, and Part C Arm 1 [Cohort 8 only]) and LV + pembrolizumab (Part C Arms 2 and 3, Cohort 8 only) as measured by investigator-determined confirmed objective response rate (ORR) using Response Evaluation Criteria in Solid Tumors version 1.1 (RECIST v1.1) for all tumor types
- For prostate cancer, evaluate antitumor activity of LV as measured by investigator-determined prostate-specific antigen (PSA) response by Prostate Cancer Clinical Trials Working Group 3 (PCWG3) criteria in addition to ORR

Secondary

- Evaluate the safety and tolerability of LV as monotherapy (Part A, Part B, and Part C Arm 1 [Cohort 8 only]) and LV + pembrolizumab (Part C Arms 2 and 3, Cohort 8 only) as measured by type, incidence, severity, seriousness, and relatedness of adverse events (AEs)
- Evaluate stability and control of disease as measured by investigator-determined disease control rate (DCR) as measured by RECIST v1.1
- Evaluate durability of response as measured by duration of response (DOR) in subjects who respond to LV as monotherapy (Part A, Part B, and Part C Arm 1 [Cohort 8 only]) and LV + pembrolizumab (Part C Arms 2 and 3, Cohort 8 only) as measured by RECIST v1.1 for all tumors, and investigator-determined PSA for prostate cancer
- Assess progression-free survival (PFS) in subjects who respond to LV as monotherapy (Part A, Part B, and Part C Arm 1 [Cohort 8 only]) and LV + pembrolizumab (Part C Arms 2 and 3, Cohort 8 only) as measured by RECIST v1.1 for all tumors, and by investigator-determined PSA for prostate cancer
- Assess survival as measured by overall survival (OS) in subjects who respond to LV as monotherapy (Part A, Part B, and Part C Arm 1 [Cohort 8 only]) and LV + pembrolizumab (Part C Arms 2 and 3, Cohort 8 only)
- Assess pharmacokinetics (PK) and immunogenicity of LV (Parts A-C)

Additional

- Assess biomarkers of biological activity, resistance, and predictive biomarkers of response

Study Population

Adult subjects with the following advanced solid tumors (Parts A, B, and C):

- Cohort 1: small cell lung cancer (SCLC) (Parts A and B)
- Cohort 2: non-small cell lung cancer-squamous (NSCLC-squamous) (Parts A and B)
- Cohort 3: non-small cell lung cancer–nonsquamous (NSCLC-nonsquamous) (Parts A and B)

- Cohort 4: head and neck squamous cell carcinoma (HNSCC) (Parts A and B)
- Cohort 5: esophageal squamous cell carcinoma (esophageal-squamous) (Parts A and B)
- Cohort 6: gastric and gastroesophageal junction (GEJ) adenocarcinoma (Parts A and B)
- Cohort 7: castration-resistant prostate cancer (CRPC) (Part B only)
- Cohort 8: melanoma (Parts B and C)

Number of Planned Subjects

Up to approximately 414 subjects will be enrolled in the entire study, including up to 72 subjects in Part A (LV 2.5 mg/kg on Day 1 of every 21-day cycle [q3wk] dosing), up to 252 subjects in Part B (LV Day 1, Day 8, and Day 15 every 21-day cycle [q1wk] dosing), and approximately 90 subjects in Part C ([Cohort 8 melanoma only] LV 1.5 mg/kg Day 1 and Day 8 but not Day 15 every 21-day cycle [2q3wk], LV 1.5 mg/kg 2q3wk + 200 mg pembrolizumab q3wk, LV 1.25 mg/kg q1wk + 200 mg pembrolizumab q3wk).

Study Design

This global, open-label, multicenter trial is designed to assess the activity, safety, and tolerability of LV monotherapy for the treatment of solid tumors. The study consists of 3 Parts evaluating subjects in 8 tumor cohorts, summarized in the table below.

- **Part A:** LV administered by intravenous (IV) infusion at a dose of 2.5 mg/kg on Day 1 of each 21-day cycle (q3wk).
- **Part B:** LV administered by IV infusion at a dose of 1.0 mg/kg (Cohort 1 through Cohort 6) or 1.25 mg/kg (Cohort 1 through Cohort 8) on Day 1, Day 8, and Day 15 of each 21-day cycle (q1wk).
- **Part C:** LV administered by IV infusion at a dose of 1.5 mg/kg on Day 1 and Day 8 of each 21-day cycle (2q3wk) as monotherapy (Arm 1) or in combination with 200 mg pembrolizumab administered by IV infusion on Day 1 of each 21-day cycle (Arm 2) or LV administered by IV infusion at a dose of 1.25 mg/kg on Day 1, Day 8, and Day 15 of each 21-day cycle (q1wk) in combination with 200 mg pembrolizumab administered by IV infusion on Day 1 of each 21-day cycle (Arm 3).

	Cohort 1: SCLC	Cohort 2: NSCLC-squamous	Cohort 3: NSCLC-nonsquamous	Cohort 4: HNSCC	Cohort 5: esophageal-squamous	Cohort 6: gastric & GEJ adenocarcinoma	Cohort 7: CRPC	Cohort 8: melanoma
Part A	X	X	X	X	X	X		
Part B	X	X	X	X	X	X	X	X
Part C								X

Subjects will be enrolled in Part A until the individual tumor cohorts have 12 subjects or activation of Protocol Amendment 1 at each respective investigative site, whichever comes first. Upon activation of Protocol Amendment 1 at each investigative site, all subsequent subjects enrolled at that site will be in Part B. Subjects in Part A may cross over to Part B with sponsor's approval based on emerging safety and efficacy data.

Part B will assess LV q1wk in the tumor cohorts. The planned dose levels in Part B are 1.0 mg/kg (Dose Level 0) and 1.25 mg/kg (Dose Level +1). Initially, approximately 12 subjects across the tumor cohorts will be enrolled and receive LV 1.0 mg/kg q1wk. Based on collective safety data from the initial 12 subjects and from the concurrently ongoing phase 1 study SGNLVA-001 evaluating LV q1wk in breast cancer, subsequent enrollment in Part B will either:

- Continue enrolling up to 12 subjects in each tumor cohort at LV 1.0 mg/kg q1wk for interim analysis for futility, or
- Enroll an additional 12 subjects across the tumor cohorts to receive LV 1.25 mg/kg q1wk (Dose Level +1) for safety analysis. If tolerability is demonstrated, enrollment will continue to 12 subjects in each tumor cohort at LV 1.25 mg/kg q1wk for interim analysis for futility.

Interim analysis for futility will be performed separately for each cohort after approximately 12 efficacy-evaluable subjects of a given cohort have been treated at a specific LV dose and schedule. Cohorts that successfully pass the interim analysis for futility may, at the sponsor's decision, continue to enroll up to an additional 18 subjects, totaling up to 30 subjects for each tumor cohort at a specific dose and schedule.

Part C will assess LV 1.5 mg/kg 2q3wk dosing as monotherapy (Arm 1), LV 1.5 mg/kg 2q3wk in combination with pembrolizumab (Arm 2), or LV 1.25 mg/kg q1wk in combination with pembrolizumab (Arm 3) dosing in subjects with melanoma (Cohort 8) only. Enrollment for Part C will begin following completion of enrollment for Part B Cohort 8 (melanoma). Each arm will enroll 30 subjects. Eligible subjects will be randomized in a 2:1:1 ratio to Arms 1, 2, and 3, respectively. Thus, of the first 60 subjects, 30 subjects will be enrolled in Arm 1, 15 subjects will be enrolled in Arm 2 and 15 subjects will be enrolled in Arm 3. This will ensure that Arm 1 reaches the target enrollment sooner. Arm 1 will be closed to further enrollment once it reaches 30 subjects, and the randomization will continue between Arm 2 and Arm 3 in a 1:1 ratio until their enrollment targets are reached.

Additional tumor types may be included in this study in future protocol amendments. Alternative dosing regimens, biopsy/biomarkers, and LV-based combinations may be tested in future amendments.

Investigational Product, Dose, and Mode of Administration

Part A (q3wk dosing): LV will be administered at a dose of 2.5 mg/kg as a 30-minute IV infusion on Day 1 of each 21-day cycle. For subjects weighing more than 100 kg, dosing will be capped at 250 mg per infusion. Any subject receiving >200 mg LV per infusion (weight >80 kg) is required to receive prophylactic granulocyte colony-stimulating factor (G-CSF).

Part B (q1wk dosing): LV will be administered at a dose of 1.0 or 1.25 mg/kg as a 30-minute IV infusion on Day 1, Day 8, and Day 15 of each 21-day cycle. The maximum dose will be 200 mg per infusion.

Part C (LV monotherapy or LV plus pembrolizumab combination):

- **Arm 1:** LV will be administered at a dose of 1.5 mg/kg as a 30-minute IV infusion 2q3wk on Day 1 and Day 8 of each 21-day cycle. The maximum dose will be 200 mg per infusion.
- **Arm 2:** LV will be administered at a dose of 1.5 mg/kg as a 30-minute IV infusion 2q3wk on Day 1 and Day 8 of each 21-day cycle. The maximum LV dose will be 200 mg per infusion. Pembrolizumab will be administered at a dose of 200 mg, approximately 60–90 minutes after administration of LV, q3wk on Day 1 of each 21-day cycle.
- **Arm 3:** LV will be administered at a dose of 1.25 mg/kg as a 30-minute IV infusion q1wk on Day 1, Day 8, and Day 15 of each 21-day cycle. The maximum LV dose will be 200 mg per infusion. Pembrolizumab will be administered at a dose of 200 mg, approximately 60–90 minutes after administration of LV, q3wk on Day 1 of each 21-day cycle.

Duration of Treatment

Subjects will continue to receive study treatment until disease progression, unacceptable toxicity, investigator decision, consent withdrawal, study termination by the sponsor, pregnancy, or death, whichever comes first.

Efficacy Assessments

For non-prostate cancer subjects, tumor assessment according to RECIST v1.1 will be performed every 6 weeks (± 3 days) for the first 12 months after the first dose of LV and then every 12 weeks (± 7 days) thereafter. Objective responses (complete response [CR] or partial response [PR]) will be confirmed with repeat scans 4 to 6 weeks after the first documentation of response. For subjects receiving pembrolizumab in Part C, investigators will make treatment decisions based on site assessments of scans using iRECIST.

For prostate cancer subjects (Part B, Cohort 7), PSA will be assessed every 3 weeks (± 3 days). Soft tissue tumor assessment by computed tomography or magnetic resonance imaging scan (CT/MRI) and bone scans according to PCWG3 criteria will be assessed every 8 weeks (± 7 days) for the first 24 weeks, then every 12 weeks (± 7 days) thereafter.

Pharmacokinetic and Immunogenicity Assessments

Subject serum and plasma samples will be obtained for LV PK and antitherapeutic antibody (ATA) evaluation at protocol-specified time points. Concentrations of LV (antibody-drug conjugate [ADC]), total antibody, and monomethyl auristatin E (MMAE) will be measured in plasma and ATA in serum.

Biomarker Assessments

Tumor samples and blood will be collected at protocol-specified time points. Target expression by immunohistochemistry (IHC) and RNA will be performed retrospectively and there will be no subject preselection. Biomarker assessments from tumor tissue may include protein expression, gene expression, disease subtype classification, tumor microenvironment, and mutational profile. Assessments in blood samples may include cytokine measurements, immunoassays, and circulating nucleic acids. Methods of analysis may include IHC, polymerase chain reaction (PCR), next-generation sequencing, multiplex immunofluorescence, flow cytometry, immunoassays, and proteomic methodologies such as enzyme-linked immunosorbent assay (ELISA) and microvesicle assessment.

Safety Assessments

Safety assessments will include the surveillance and recording of AEs, physical examination findings, vital signs, concomitant medications, pregnancy testing, and laboratory tests. An ongoing, real-time review of subject safety and serious adverse events (SAEs) will be conducted by the sponsor's Drug Safety Department. Adverse event (AE) severity will be graded using the National Cancer Institute Common Terminology Criteria for Adverse Events (NCI CTCAE), version 5.

Statistical Methods

The primary analysis of the study will be performed separately for each cohort in Parts A, B, and C when all treated subjects in the cohort have been followed for at least 6 months or come off study, whichever comes first. The primary efficacy endpoint of confirmed ORR per RECIST v1.1 will be estimated for each cohort based on the full analysis set (FAS), comprising all subjects who received any amount of study treatment. The point estimate of ORR and 90% exact confidence intervals (CIs) using the Clopper-Pearson method will be provided for each cohort.

For the prostate cancer cohort, the confirmed PSA response rate and 90% exact CI will also be presented. The confirmed PSA response is defined as a reduction from baseline PSA level of at least 50%, measured twice ≥ 3 weeks apart.

Interim futility analyses will be performed separately for each cohort in Part A and Part B after approximately 12 subjects of a given cohort have been treated with a specific LV dose and schedule (LV q3wk at 2.5 mg/kg, LV q1wk at 1.0 mg/kg, or LV q1wk at 1.25 mg/kg) and are efficacy evaluable post-baseline. Enrollment to each cohort may be held after approximately 12 subjects for interim futility analysis of the respective cohorts. The Bayesian predictive probability of success (PPoS) approach will be used to determine the futility criteria. At the time of each interim analysis, the PPoS will be calculated. A PPoS $< 10\%$ (i.e., ≤ 1 response among the first 12 subjects, or ≤ 3 responses among the first 12 prostate cancer subjects) indicates that it is unlikely the ORR will be better than the response rate of current standard of care at the end of the cohort given the interim result. Based on efficacy and safety data, together with the PPoS, a cohort may be stopped early by the sponsor. A cohort may also be discontinued at any point at the discretion of the sponsor.

Safety measurements will be summarized by descriptive statistics based on the safety analysis set. The safety analysis set will include all subjects who received any amount of study treatment.

For all the parts, the sample size is not based on power calculation for a formal hypothesis testing but is selected to provide a degree of characterization of commonly occurring AEs in the safety profile and/or a reasonable estimation precision of ORR.

For a sample size of 30 subjects per cohort/arm, assuming confirmed ORR and confirmed PSA response rate for CRPC is between 10% and 50%, the 2-sided 90% exact CI are summarized below:

Confirmed ORR*	90% Exact CI (N=30)
10%	(3%, 24%)
20%	(9%, 36%)
30%	(17%, 47%)
40%	(25%, 57%)
50%	(34%, 66%)

*Including confirmed PSA response rate for CRPC cohort

TABLE OF CONTENTS

PROTOCOL SYNOPSIS	2
LIST OF ABBREVIATIONS AND DEFINITIONS OF TERMS	13
1. INTRODUCTION	18
1.1. LIV-1	18
1.2. Ladiratuzumab vedotin	18
1.2.1. Mechanism of Action	18
1.2.2. Summary of Preclinical Activity	19
1.2.3. Summary of Nonclinical Toxicology	19
1.2.4. Summary of Clinical Study SGNLVA-001: A Phase 1 Trial of LV in Subjects With Locally Advanced/Metastatic Breast Cancer	20
1.2.4.1. Study Design of SGNLVA-001	20
1.2.4.2. DLTs and Maximum Administered Dose	20
1.2.4.3. Safety in SGNLVA-001	20
1.2.4.4. Preliminary Efficacy Data for SGNLVA-001	22
1.3. Pembrolizumab Background.....	25

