5.2.3. Dose and Administration

LV is administered by IV infusion given over approximately 30 minutes. LV must not be administered as an IV push or bolus. In the absence of infusion-related reactions (IRR), the infusion rate for all subjects should be calculated in order to achieve a 30-minute infusion period.

However, given the variability of infusion pumps from site to site, a window between -5 minutes and +10 minutes is permitted (i.e., infusion time is 30 minutes -5 min/+10 min).

LV can be administered via central venous access line (preferred) or peripheral IV. Clinical site staff should monitor the infusion site closely for redness, swelling, pain, and infection during and at any time after administration. Advise subjects to report redness or discomfort promptly at the time of administration or after infusion. The IV bag containing LV should not be mixed with other medications.

Dosing is based on the subject's actual body weight at the beginning of each cycle.

Detailed instructions for dose preparation are provided in the Pharmacy Instructions.

Part A (q3wk dosing): LV at a dose of 2.5 mg/kg (maximum dose of 250 mg per infusion) will be administered on Day 1 of each 21-day cycle by IV infusion given over approximately 30 minutes. **For subjects weighing greater than 100 kg, dose calculations will be based on 100 kg for these individuals (including dose reductions).** Rounding is permissible within 1 mg of nominal dose. Any subject receiving >200 mg LV per infusion (weight >80 kg) is required to receive prophylactic G-CSF.

Part B (q1wk dosing): LV at a dose of 1.0 or 1.25 mg/kg will be administered on Day 1, Day 8, and Day 15 of each 21-day cycle. The maximum dose will be 200 mg per infusion.

Part C (2q3wk or q1wk dosing): LV at a dose of 1.5 mg/kg will be administered on Day 1 and Day 8 but not Day 15 of each 21-day cycle (2q3wk) for Arm 1 and Arm 2. LV at a dose of 1.25 mg/kg will be administered on Day 1, Day 8, and Day 15 of each 21-day cycle (q1wk) for Arm 3. The maximum dose of LV for all 3 arms will be 200 mg per infusion. For Arm 2 and Arm 3, pembrolizumab infusion must start approximately 60–90 minutes after administration of LV (see Section 5.3.3).

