5.2.4.2. Part B (q1wk dosing) and Part C (Arm 3; q1wk dosing)

In the event of an AE or lab criteria that prevents dosing of LV (see Section 5.2.3.1), the LV dose for the week should be withheld. LV may be resumed when the dosing criteria are met. If a dose(s) of LV is withheld, the corresponding visit may be skipped and resume the following week (eg, if the Day 8 dose is skipped, visits will resume on Day 15; if Day 8 and Day 15 doses are skipped, visits will resume on Day 1 of the following cycle). Day 1 of a cycle may be delayed but not skipped.

Dose reduction of LV may be considered in the event of recurrent AE despite withheld doses. Dose re-escalation following dose reduction is not allowed. Dose levels for LV dose reductions in Part B and Part C (Arm 3) are shown in [Table 11](#).

For Part C (Arm 3), subjects who discontinue pembrolizumab due to a pembrolizumab-related AE (see Section 5.3.4) may continue LV. Similarly, subjects who discontinue LV for a LV-related AE may continue pembrolizumab. See Section 5.5.3 for details on managing overlapping AEs.

Table 11: Q1wk LV dose reductions

Starting Dose	First Dose Reduction (mg/kg/wk)	Second Dose Reduction (mg/kg/wk)
Starting dose 1.0 mg/kg/wk	0.75	0.5
Starting dose 1.25 mg/kg/wk	1.0	0.75

For nonclinical events requiring alteration in dosing schedule (eg, holidays, scheduling conflicts), a +2 day dosing window is allowed. Nonclinical events that require skipping a dose(s), must be approved by sponsor medical monitor. At least 7 days must elapse between each administration of LV.

Dose modification guidelines for LV q1wk treatment-associated toxicity are detailed in [Table 12](#).

Table 12: Dose modifications for LV treatment-associated toxicity (Part B and Part C [Arm 3] q1wk dosing)

Toxicity	Grade 1	Grade 2	Grade 3	Grade 4
Peripheral neuropathy ^a	Continue at same dose level	Withhold until toxicity resolves to \leq Grade 1; treatment may resume at the next lower dose level (see Table 11)	Withhold until toxicity resolves to \leq Grade 1, then resume treatment at the next lower dose level (see Table 11)	Discontinue treatment
Hyperglycemia		Hold for blood glucose >250 mg/dL or >13.9 mmol/L. Resume treatment once elevated blood glucose has improved to ≤ 250 mg/dL or ≤ 13.9 mmol/L and subject is clinically and metabolically stable (see Section 5.6 for details).		

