Non-hematologic ^a (except peripheral neuropathy and hyperglycemia)	Continue at same dose level	Continue at same dose level	Withhold dose until toxicity is \leq Grade 2 or has returned to baseline, then resume treatment at same dose level ^b	Withhold dose until toxicity is \leq Grade 2 or has returned to baseline, then reduce dose to the next lower dose level (see Table 11) and resume treatment, or discontinue at the discretion of the investigator ^{b,c}
Hematologic ^a	Continue at same dose level	Continue at same dose level	Withhold until toxicity resolves to \leq Grade 2 or baseline ^{d,e} , then resume treatment at the same dose level. If the dose is held >48 hours, the dose may be omitted and dosing may resume on the next scheduled dosing day. See Sections 5.4.2 and 5.4.3 on allowed concomitant therapy and myeloid growth factors.	Withhold until toxicity resolves to \leq Grade 2 or baseline ^{d,e} , then reduce dose to the next lower dose level (see Table 11) if treatment is resumed ^{b,c} . If the dose is held >48 hours, the dose may be omitted and dosing may resume on the next scheduled dosing day. If Grade 4 neutropenia recurs, reduce dose to the next lower dose level (see Table 11) if treatment is resumed, or discontinue at the discretion of the investigator. See Sections 5.4.2 and 5.4.3 on allowed concomitant therapy and myeloid growth factors.
Febrile neutropenia ^a	Not applicable	Not applicable	Withhold until febrile neutropenia resolves and neutrophil count returns to \leq Grade 2 or baseline and then resume treatment at the next lower dose level (see Table 11). If the dose is held >48 hours, the dose may be omitted and dosing may resume on the next scheduled dosing day. If febrile neutropenia recurs, reduce dose to the next lower dose level (see Table 11) if treatment is resumed, or discontinue at the discretion of the investigator. See Sections 5.4.2 and 5.4.3 on allowed concomitant therapy and myeloid growth factors.	

The maximum dose will be 200 mg per infusion for subjects enrolled in Part B and Part C (Arm 3).

- a Only 2 dose reductions are allowed without prior medical monitor approval. Additional toxicities should be managed with dose delays. Medical monitor approval is needed for further dose reduction.
- b Subjects who develop Grade 3 or 4 electrolyte laboratory abnormalities may continue study treatment without interruption if a management plan consistent with institutional practice and regular monitoring are put in place.

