If a subject has a clinically significant, unresolved AE on Day 1 of C2 or beyond, the start of the cycle may be delayed for up to 14 days. Delays of >14 days must be approved by the medical monitor.

In the event a subject is unable to tolerate their dose level, additional treatment cycles (C2 or later) may be administered at a lower dose level upon approval by the medical monitor.

Table 14: Dose modifications for LV-associated toxicity (Part C [Arms 1 and 2]; 2q3wk dosing)

Toxicity	Grade 1	Grade 2	Grade 3	Grade 4
Peripheral neuropathy ^a	Continue at same dose level	Withhold until toxicity resolves to \leq Grade 1; then resume treatment at the next lower dose level (see Table 13)	Withhold until toxicity resolves to \leq Grade 1, then resume treatment at the next lower dose level (see Table 13)	Discontinue treatment
Hyperglycemia			Hold for blood glucose >250 mg/dL or >13.9 mmol/L. Resume treatment once elevated blood glucose has improved to ≤ 250 mg/dL or ≤ 13.9 mmol/L and subject is clinically and metabolically stable (see Section 5.6 for detail).	
Non-hematologic ^a (except peripheral neuropathy and hyperglycemia)	Continue at same dose level	Continue at same dose level	Withhold dose until toxicity is \leq Grade 2 or has returned to baseline, then resume treatment at same dose level ^b	Withhold dose until toxicity is \leq Grade 2 or has returned to baseline, then reduce dose to the next lower dose level (see Table 13) and resume treatment, or discontinue at the discretion of the investigator ^{b,c}
Hematologic ^a	Continue at same dose level	Continue at same dose level	Withhold until toxicity resolves to \leq Grade 2 or baseline ^{d,e} . For neutropenia, strongly consider G-CSF support , then resume treatment at the same dose level. Prophylactic G-CSF support should be strongly considered for subsequent cycles. (See Appendix G)	Withhold until toxicity resolves to \leq Grade 2 or baseline ^{d,e} . For neutropenia, strongly consider G-CSF support , then resume treatment at the same dose level. Prophylactic G-CSF support is required for all subsequent cycles. If Grade 4 neutropenia recurs despite G-CSF support, consider dose reduction to dose level -1 (see Table 13) or discontinuation. (Appendix G)

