Febrile neutropenia ^a			G-CSF support is required for treatment of febrile neutropenia. Withhold until febrile neutropenia resolves and neutrophil count returns to \leq Grade 2 or baseline then resume treatment at the same dose level. Prophylactic G-CSF is required for all subsequent cycles. If febrile neutropenia recurs despite G-CSF factor support, consider dose reduction to dose level -1 (see Table 13) or discontinuation.	

The maximum dose will be 200 mg per infusion for patients enrolled in Part C.

a Only 2 dose reductions are allowed without prior medical monitor approval. Additional toxicities should be managed with dose delays. Medical monitor approval is needed for further dose reduction.

b Subjects who develop Grade 3 or 4 electrolyte laboratory abnormalities may continue study treatment without interruption if a management plan consistent with institutional practice and regular monitoring are put in place.

c Treatment should be discontinued for subjects who experience Grade 4 infusion-related reactions.

d Support with blood product transfusions allowed per institutional standard of care.

e Subjects who develop Grade 3 or 4 lymphopenia may continue study treatment without interruption.

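### In Part C Arms 1 and 2 (and, more remotely, weekly dosing) the single 200 mg cap shrinks or cancels the first LV dose reduction in very heavy subjects; a minor gap in the dose-modification rule

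*Protocol*

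**What the plan says.** The Protocol synopsis gives LV in Part C Arm 1 at 1.5 mg/kg "on Day 1 and Day 8 of each 21-day cycle. The maximum dose will be 200 mg per infusion". Protocol Section 5.2.3 bases the LV dose on "actual body weight at the beginning of each cycle". For Part C it adds: "The maximum dose of LV for all 3 arms will be 200 mg per infusion". The synopsis and Section 5.1 give the same limit for Parts B and C.

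The limit is repeated, unchanged, under the dose-modification tables. The note to Table 14 (Arms 1 and 2) reads "The maximum dose will be 200 mg per infusion for patients enrolled in Part C", and the note to Table 12 (weekly dosing) reads "The maximum dose will be 200 mg per infusion for subjects enrolled in Part B and Part C (Arm 3").

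Tables 13 and 11 list the reduced levels in mg/kg only:

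- Arms 1 and 2: 1.5, 1.25, 1.0 mg/kg, with 0.75 on medical monitor approval.
- Weekly from 1.25: 1.25, 1.0, 0.75 mg/kg.
- Weekly from 1.0: 1.0, 0.75, 0.5 mg/kg.

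For Grade 2 or 3 neuropathy in Arms 1 and 2, Table 14 directs that LV be withheld until recovery, and "then resume treatment at the next lower dose level (see Table 13"). For Grade 4 non-hematologic toxicity it directs reduction or discontinuation. On the weekly schedule, Table 12 says for Grade 3 neuropathy "then resume treatment at the next lower dose level (see Table 11"). It also requires the lower level after Grade 4 hematologic toxicity or febrile neutropenia if treatment resumes. For Grade 2 neuropathy on the weekly schedule, resumption at the lower level is only permitted.

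Part A is written differently. Table 9 pairs 2.5, 2.0 and 1.5 mg/kg with maxima of 250, 200 and 150 mg. Section 5.2.3 doses subjects over 100 kg as if they weighed 100 kg, reductions included.

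**The concern.** A reduction after toxicity is meant to lower the dose the subject receives. Under a cap that does not fall with the level, a subject whose starting dose is already capped has the reduced level calculated on full weight and then cut off at the same 200 mg. The step becomes smaller and, at a high enough weight, disappears. Staff who follow the table exactly could record a reduction and give the same milligrams that preceded the toxicity. That empty step also appears to use up one of the two reductions allowed without medical monitor approval (note a to Tables 12 and 14). Part A shows that the sponsor has a rule that prevents this for the same drug. Parts B and C do not carry it over, and no reason is given.

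**Working it through.** **Inputs.** Cap 200 mg (5.2.3; notes to Tables 12 and 14). Dose levels from Tables 11 and 13. Part A maxima from Table 9. No eligibility criterion limits body weight.

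**Check against the Protocol's own Part A figures.** 200 / 2.5 = 80 kg, the weight at which prophylactic G-CSF becomes mandatory. 100 kg x 2.5, 2.0 and 1.5 mg/kg = 250, 200 and 150 mg, as in Table 9. At 120, 160 or 200 kg the Part A doses stay at 250/200/150 mg, so the steps remain 20% and 25%.

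**Formula for Parts B and C.** Delivered dose = min(level x weight, 200). The step is smaller than nominal above 200 / starting level and absent from 200 / reduced level.

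| First reduction | Nominal step | Smaller above | Absent from |
|---|---|---|---|
| Arms 1 and 2: 1.5 to 1.25 | 1 - 1.25/1.5 = 16.7% | 200/1.5 = 133.3 kg | 200/1.25 = 160 kg |
| Weekly: 1.25 to 1.0 | 1 - 1.0/1.25 = 20% | 160 kg | 200/1.0 = 200 kg |
| Weekly: 1.0 to 0.75 | 1 - 0.75/1.0 = 25% | 200 kg | 200/0.75 = 266.7 kg |

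Delivered doses:

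| Schedule | Weight (kg) | Start / 1st / 2nd level (mg) | 1st step | 2nd step |
|---|---|---|---|---|
| Arms 1 and 2 | 140 | 200 / 175 / 140 | 12.5% | 20% |
| Arms 1 and 2 | 150 | 200 / 187.5 / 150 | 6.25% | 20% |
| Arms 1 and 2 | 160 | 200 / 200 / 160 | 0% | 20% |
| Arms 1 and 2 | 180 | 200 / 200 / 180 | 0% | 10% |
| Arms 1 and 2 | 200 | 200 / 200 / 200 | 0% | 0% |
| Weekly, 1.25 | 180 | 200 / 180 / 135 | 10% | 25% |
| Weekly, 1.25 | 200 | 200 / 200 / 150 | 0% | 25% |

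**How many subjects.** The documents give no weight distribution. Assumption: mean 75 to 90 kg and SD 15 to 22 kg, either normal or log-normal with the same mean and SD.

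- Arms 1 and 2 (2 x 30 = 60 subjects), above 133.3 kg: normal 0.005% to 2.44%, or 0.003 to 1.5 subjects; log-normal 0.13% to 3.99%, or 0.08 to 2.4 subjects.
- Arms 1 and 2, above 160 kg: at most 0.073% (normal) or 0.61% (log-normal), or 0.04 or 0.36 subjects.
- 1.25 mg/kg weekly: at most 240 in Part B (252 less the initial 12 at 1.0 mg/kg) plus 30 in Arm 3 = 270. Above 160 kg: at most 0.2 (normal) or 1.6 (log-normal). Above 200 kg: at most 0.030% x 270 = 0.08.
- 1.0 mg/kg weekly: if only the initial 12 receive it, 0.030% x 12 = about 0.004 above 200 kg. This case is theoretical.

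These counts rest on weight alone. The subject must also have a toxicity that triggers a reduction, so the number affected would be smaller still.

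**The case against.** The strongest reply is that nothing printed is wrong. Tables 11 and 13 define levels in mg/kg and promise no milligram step. A capped subject is never dosed above the listed level: at 160 kg, 200 mg is 1.25 mg/kg, so that subject has received the first reduced level since Cycle 1. This stands. A reader might infer an arithmetic error or overdosing, and the documents support neither.

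A reader might also infer that such a subject cannot get a lower dose. That is not so. LV is withheld first, and discontinuation is open for some events. The second listed reduction works at 160 kg in Arms 1 and 2 (160 mg) and at 200 kg on 1.25 mg/kg weekly (150 mg). For Arms 1 and 2, Section 5.2.4.3 says "additional treatment cycles (C2 or later) may be administered at a lower dose level upon approval by the medical monitor", and Table 13 notes a and b allow further steps by agreement with the monitor. Table 12 note a allows monitor-approved further reduction on the weekly schedule. These safeguards soften the rule but do not repair it, since the directed first step can still change nothing. At 200 kg in Arms 1 and 2 both listed steps are empty, and the first real cut (0.75 mg/kg, 150 mg) needs approval.

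Section 3.2.2 is also relevant. In q3wk dosing at 2.5 mg/kg, 5 of 11 subjects above 200 mg had neutropenia-associated SAEs, against none of 18 below 200 mg. Parts B and C never exceed 200 mg, so the Part A precedent is only partly comparable. Those data cannot be read as evidence of harm from an unreduced 200 mg dose either.

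Finally, the Pharmacy Instructions, which are not among the documents, may address reduced-dose maxima. But the Protocol tables direct the dose, and Part A states its caps in the Protocol.

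**Conclusion.** The point holds as a minor, low-priority gap in a dose-modification rule, mainly in Part C Arms 1 and 2. There the first reduction falls short of 16.7% above 133.3 kg and is absent from 160 kg. The same gap exists at 1.25 mg/kg weekly above 160 kg, absent from 200 kg, with even smaller expected numbers of subjects who lose the step entirely.

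The thresholds follow from the Protocol text alone. The subject counts (at most about 2.4 and 0.4 of 60 in Arms 1 and 2) rest on assumed weights, and the upper ends come from the most extreme combination: mean 90 kg, SD 22 kg, log-normal. The documents contain no toxicity comparison between milligram doses at or below 200 mg, so no size of harm can be stated. Sample size and the efficacy analyses are unaffected.

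**What to change.** Add a maximum-dose column to Tables 13 and 11, modelled on Table 9, with matching notes under Tables 12 and 14, in Section 5.2.3 and in the pharmacy instructions. A cap of 200 x level / starting level preserves each nominal step:

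- Arms 1 and 2, 1.5/1.25/1.0 mg/kg: 200 / 166.7 / 133.3 mg.
- Weekly, 1.25/1.0/0.75 mg/kg: 200 / 160 / 120 mg.

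These values are examples; the sponsor's clinical team should set the final ones.

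The cost is a few lines of text and a lower mg/kg dose for very heavy subjects after a reduction. In Arms 1 and 2 a 160 kg subject would get 1.04 then 0.83 mg/kg (166.7/160, 133.3/160) instead of 1.25 then 1.0. At 200 kg the figures are 0.83 then 0.67 mg/kg, instead of 1.0 at both levels. The 0.67 lies below the 0.75 mg/kg level that now needs medical monitor approval, so the clinical team should decide whether that is acceptable or whether approval should apply there too. Part A already accepts this kind of trade. Subjects whose starting dose is not capped are unaffected.
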